6.1.4 Response Criteria

6.1.4.1 Evaluation of Target Lesions

Complete Response (CR)

Disappearance of all target lesions. Any pathological lymph nodes (whether target or non-target) must have reduction in short axis to < 10 mm.

Partial Response (PR)

At least a 30% decrease in the sum of the diameters of target lesions, taking as reference the baseline sum diameters

Progressive Disease (PD)

At least a 20% increase in the sum of the diameters of target lesions, taking as reference the smallest sum on study (this includes the baseline sum if that is the smallest on study). In addition to the relative increase of 20%, the sum must also demonstrate an absolute increase of at least 5 mm.

NOTE: The appearance of one or more new lesions is also considered progression, See Section [6.1.4.3](#).

Stable Disease (SD)

Neither sufficient shrinkage to qualify for PR nor sufficient increase to qualify for PD, taking as reference the smallest sum diameters while on study. (Note: a change of 20% or more that does not increase the sum of the diameters by 5 mm or more is coded as stable disease)

To be assigned a status of stable disease, measurements must have met the stable disease criteria at least once after study entry at a minimum interval of 6 weeks.

6.1.4.2 Evaluation of Non-Target Lesions

Complete Response (CR)

Disappearance of all non-target lesions. All lymph nodes must be non-pathological in size (< 10 mm short axis)

Non-CR/Non-PD

Persistence of one or more non-target lesion(s).

Progressive Disease (PD)

Appearance of one or more new lesions and/or unequivocal progression of existing non-target lesions (see Section [6.1.4.3](#)). Unequivocal progression should not normally trump target lesion status. It must be representative of overall disease status change, not a single lesion increase.

When the patient also has measurable disease, there must be an overall level of substantial worsening in non-target disease such that, even in the presence of SD or PR in target disease, the overall tumor burden has increased sufficiently to merit discontinuation of therapy. A modest "increase" in the size of one or more non-target lesions is usually not sufficient to qualify for unequivocal progression status. The designation of overall progression solely on the basis of change in non-target disease in the face of SD or PR of target disease will therefore be extremely rare.

When the patient only has non-measurable disease, the increase in overall disease burden should be comparable in magnitude to the increase that would be required to

declare PD for measurable disease: i.e., an increase in tumor burden from “trace” to “large”, an increase in nodal disease from “localized” to “widespread”, or an increase sufficient to require a change in therapy.

Although a clear progression of “non-target” lesions only is exceptional, the opinion of the treating physician should prevail in such circumstances, and the progression status should be confirmed at a later time by the review panel (or Principal Investigator).

6.1.4.3 Evaluation of New Lesions

The appearance of new lesions constitutes Progressive Disease (PD).

A growing lymph node that did not meet the criteria for reporting as a measurable or non-measurable lymph node at baseline should only be reported as a new lesion (and therefore progressive disease) if it:

- a) increases in size to ≥ 15 mm in the short axis, or
- b) there is new pathological confirmation that it is disease (regardless of size).

new effusion or ascites that appears during treatment should only be reported as a new lesion (and therefore progressive disease) if it has cytological confirmation of malignancy.

6.1.4.4 Evaluation of Best Overall Response

The best overall response is the best response recorded from the start of the treatment until disease progression/recurrence or non-protocol therapy (taking as reference for progressive disease the smallest measurements recorded since the treatment started). The patient’s best response assignment will depend on the achievement of both measurement and confirmation criteria.

For Patients with Measurable Disease (i.e., Target Disease)

Target Lesions	Non-Target Lesions	New Lesions*	Best Overall Response	Remarks
CR	CR	No	CR	
CR	Non-CR/Non-PD***	No	PR	
CR	Not evaluated	No	PR	
PR	Non-PD***/not evaluated	No	PR	
SD	Non-PD***/not evaluated	No	SD	Documented at least once ≥ 6 wks. from study entry
PD	Any	Yes or No	PD	No prior SD, PR or CR
Any	PD**	Yes or No	PD***	
Any	Any	Yes	PD	

* See RECIST 1.1 manuscript for further details on what is evidence of a new lesion.

** In exceptional circumstances, unequivocal progression in non-target lesions may be accepted as disease progression.

*** PD in non-target lesions should not normally trump target lesion status. It must be representative of overall disease status change, not a single lesion increase. Please refer to the Evaluation of Non-Target Lesions – Progressive Disease section for further explanation.

NOTE: Patients with a global deterioration of health status requiring discontinuation of treatment without objective evidence of disease progression at that time should be reported as “*symptomatic deterioration*.” Every effort should be made to document the objective progression even after discontinuation of treatment.

6.1.4.5 Duration of Response

Duration of Overall Response

The duration of overall response is measured from the time measurement criteria are met for CR or PR (whichever is first recorded) until the first date that recurrent or progressive disease is objectively documented (taking as reference for progressive disease the smallest measurements recorded since the treatment started).

The duration of overall CR is measured from the time measurement criteria are first met for CR until the first date that progressive disease is objectively documented.

Duration of Stable Disease

Stable disease is measured from the start of the treatment until the criteria for progression are met, taking as reference the smallest measurements recorded since the treatment started, including the baseline measurements.

To be assigned a status of stable disease, measurements must have met the stable disease criteria at least once after study entry at a minimum interval of 6 weeks.

Rev. Add3 **7. Study Parameters**

Rev. Add1
Rev. Add4

7.1 Therapeutic Parameters

1. Pre- study screening CT scans and MRIs used to assess all measurable or non-measurable sites of disease must be done within 4 weeks prior to randomization/registration.
2. Pre-study screening CBC (with differential and platelet count) and chemistries as outlined in Section [3.1](#) should be done \leq 1 week before randomization/registration. All other pre-study screening labs should be done within 2 weeks prior to randomization/registration. Screening assessments performed \leq 72 hours before Cycle 1, Day 1 are not required to be repeated for Cycle 1, Day 1.
3. Please see Section [5.1](#) for more information on treatment administration parameters.

Therapeutic parameters	Pre-study screening	Cycle 1 Day 1	Cycle 2 Day 1	Cycle 3 Day 1	Cycle 4 Day 1	Maintenance Nivolumab Cycle 5+ Day 1, 15, 29	Observation (Arm B) ¹¹	Post Treatment/Observation ¹² to 5 years from study entry
Full Medical History	X							
Interval History ¹		X	X	X	X	X	X	X
Vital signs including weight ¹	X	X	X	X	X	X	X	X
Performance status ¹	X	X	X	X	X	X	X	X
CBC with Differential ²	X	X	X	X	X	X	X ¹¹	
Serum chemistry ²	X	X	X	X	X	X	X ¹¹	
TSH, reflex free T3, reflex free T4 ³	X	X		X		X ³		
Amylase ⁴		X						
Lipase ⁴		X						
HIV, HBV, HCV serology ⁵	X							
Pregnancy Test ⁶	X							
EKG ⁷	X							
Urinalysis ⁸	X	X	X	X	X	X ⁸		
CT chest ⁹	X			X		X	X	X
CT abdomen ⁹	X			X		X	X	X
CT pelvis ⁹	X			X		X	X	X
MRI brain ¹⁰	X							

1. At subsequent visits, symptom-directed history and physical examinations including vital signs, weight and performance status should be performed. Symptom-directed history, physical exam and performance status may be performed up to 72 hours prior to each cycle.
2. CBCs (with differential and platelet count) which includes WBC, ANC, Platelets, Hgb, and Hct, and chemistry to include Albumin, alkaline phosphatase, total bilirubin, carbon dioxide, BUN, calcium, chloride, creatinine, glucose, LDH, phosphorus, potassium, total protein, SGOT [AST], SGPT [ALT], sodium, required for protocol therapy must be done \leq 72 hours prior to treatment administration. Magnesium is only required for patients receiving cisplatin on day 1 of each cycle that cisplatin is administered. For cycle 1 day 1, need not be repeated if the screening labs were done within 72 hours of treatment administration.
3. TSH, reflex free T3 and reflex free T4 will be done at screening as clinically indicated. For the Nivolumab Arm only, these tests will also be done on C1D1, C3D1, C5D1, and every 8 weeks during the maintenance phase. Thyroid labs collected at screening do not need to be repeated at C1D1 if done within 72 hours of treatment administration.
4. Amylase, lipase will be required for patients receiving nivolumab on C1D1 and when clinically indicated.
5. All patients will be tested for HIV, hepatitis B and hepatitis C at screening, if clinically indicated.
6. Blood or Urine pregnancy test (women of childbearing potential). All women of childbearing potential must have a negative pregnancy test (sensitivity of at least 50 mIU/mL). The pregnancy test must be performed within 14 days prior to registration.
7. All patients will have an EKG at screening, if clinically indicated. Patients randomized to the Nivolumab Arm will have troponin as clinically indicated. Further cardiac evaluation is recommended including troponin, EKG, echocardiogram, and cardiology consult when clinically indicated.
8. Urinalysis will be required at screening for all patients and on day 1 of every cycle on the Nivolumab Arm. It does not need to be performed on days 15 or 29 for Cycle 5+.
9. Screening assessments will include CT chest and abdomen. CT pelvis should be performed as clinically indicated. On study and follow-up assessments will include a CT chest and abdomen at each time point, and CT pelvis as clinically indicated. For both Arm A and Arm B, all patients will be evaluated for response while on study using radiographic evaluations with tumor measurements every 6 weeks (+/- 7 days) for the first 6 months on study, every 8 weeks (+/- 7 days) until 1 year on study, and then every 12 weeks (+/- 7 days) after 1 year on study until the patient discontinues protocol treatment (Arm A) or the end of observation (Arm B) and enters follow-up (see footnote 12 for follow-up schedule). Documentation (radiologic) must be provided for patients removed from study for progressive disease. For all patients on Arm A and Arm B, CT scans will be done until disease progression.
10. Head CT allowed, if patient cannot tolerate MRI. Brain imaging will be done at screening and then as clinically indicated.
11. For Arm B patients on observation, symptom-directed history and physical examinations including vital signs, weight and performance status should be performed every 6 weeks (+/- 7 days) for the first 6 months on study, then every 8 weeks (+/- 7 days) until 1 year on study; and every 12 weeks (+/- 7 days) after 1 year on study, alongside the radiologic evaluations. Labs (CBC w/diff, serum chemistries) are done as clinically indicated. CT scans will be done until disease progression
12. Follow-up after patient discontinues protocol treatment (Arm A) or the end of observation (Arm B): every 3 months for patients < 2 years from registration, every 6 months if patient is 2-3 years from registration, and yearly until 5 years from registration. Patients in the observation phase on Arm B may be seen more frequently per schedule of CT scans as per footnote 9. All patients, including those who discontinue protocol therapy early, will be followed for response until progression, even if non-protocol therapy is initiated, and for survival for 5 years from the date of registration. For all patients during follow-up, symptom-directed history and physical examinations including vital signs, weight and performance status should be performed until progression. Follow-up for survival after progression may occur via phone calls.

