6.1 Antitumor Effect – Solid Tumors

For the purposes of this study, patients should be re-evaluated for response every 6 weeks. All patients will be evaluated for response every 6 weeks for the first 6 months on study, every 8 weeks until 1 year on study, and then every 12 weeks after 1 year on study.

Response and progression will be evaluated in this study using the international criteria proposed by the revised Response Evaluation Criteria in Solid Tumors (RECIST) guideline (version 1.1) [Eur J Ca 45:228-247, 2009]. Changes in the largest diameter (unidimensional measurement) of the tumor lesions and the shortest diameter in the case of malignant lymph nodes are used in RECIST.

The following general principles must be followed:

1. To assess objective response, it is necessary to estimate the overall tumor burden at baseline to which subsequent measurements will be compared. All baseline evaluations should be performed as closely as possible to the beginning of treatment and never more than four weeks before registration.
2. Measurable disease is defined by the presence of at least one measurable lesion.
3. All measurements should be recorded in metric notation by use of a ruler or calipers.
4. The same method of assessment and the same technique must be used to characterize each identified lesion at baseline and during follow-up.

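### Minor: once protocol treatment stops, footnotes 9 and 12 of Section 7.1 space CT scans differently by arm, so the rule that dates PFS depends on treatment; the effect is small and the repair is cheap

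*Combined protocol and SAP*

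**What the plan says.** Footnote 9 of Section 7.1 starts with one calendar for both arms: "every 6 weeks (+/- 7 days) for the first 6 months on study", then 8-weekly to one year and 12-weekly after that. It runs the calendar "until the patient discontinues protocol treatment (Arm A) or the end of observation (Arm B) and enters follow-up (see footnote 12 for follow-up schedule". Footnote 12 then sets the interval: "Follow-up after patient discontinues protocol treatment (Arm A) or the end of observation (Arm B): every 3 months" up to two years from registration, 6-monthly from two to three years, and yearly to five. It exempts one group only: "Patients in the observation phase on Arm B may be seen more frequently per schedule of CT scans as per footnote 9".

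The Arm B table notes in Section 5.1 have observation end at progression or at the start of other treatment. The end of chemotherapy does not end it.

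Footnote 9 also says "For all patients on Arm A and Arm B, CT scans will be done until disease progression" and "On study and follow-up assessments will include a CT chest and abdomen at each time point".

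Section 6.1 makes no distinction by arm or by treatment status. It says first that "patients should be re-evaluated for response every 6 weeks" and then gives the detailed rule: "All patients will be evaluated for response every 6 weeks for the first 6 months on study", followed by 8 and 12 weeks.

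Sections 5.5 and 5.7 require follow-up to progression after early discontinuation but give no interval. Section 9.2 dates PFS from documented progression or death. Sections 9.2 and 9.3 contain no adjustment for unequal scan spacing.

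**The concern.** Most PFS dates in this trial will be scan dates. If progression-free patients are scanned less often in one arm, progression there is recorded later on average and the arm gains apparent PFS without any treatment effect. Here the less frequent schedule falls on Arm A patients who have left treatment without progressing.

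The protocol creates that group. The nivolumab rules in Section 5.4.2 take patients off protocol therapy for many grade 3-4 events, and Arm B has no equivalent route. The group includes patients who stop nivolumab for toxicity and finish chemotherapy. Section 5.4.2 lets chemotherapy continue, but Section 5.1 caps it at four cycles and Arm A maintenance is nivolumab alone. After cycle 4, at about week 12, these patients have no protocol treatment left.

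Patients who start non-protocol therapy leave the dense calendar in either arm (Sections 5.1 and 5.6), so they do not contribute to the contrast.

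**Working it through.** **1. The two rules side by side**, for a progression-free patient who is off protocol treatment and on no new therapy:

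| Time on study | Arm A (footnote 12) | Arm B, observation (footnote 9) |
|---|---|---|
| 0-6 months | 3 months, about 13 weeks | 6 weeks |
| 6-12 months | about 13 weeks | 8 weeks |
| Year 2 | about 13 weeks | 12 weeks |
| Years 2-3 | 6 months | 12 weeks |

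Footnote 12 gives a visit interval and does not itself mention CT every 3 months. The CT reading follows from footnote 9's pointer to footnote 12, its CT at each follow-up time point, and the CT marks in the post-treatment column of the table. The last row matters little, because Section 9.5 plans a total duration of 25 months.

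**2. Detection delay.** On average, progression is found about half an interval late: 13/2 = 6.5 weeks against 3 or 4 weeks in year 1, a difference of 2.5 to 3.5 weeks. In year 2 it is 6.5 against 6. Simulated year-1 means run from 1.7 to 4.6 weeks later, and 20-37% of affected progressions are found earlier because the 3-monthly dates fall differently.

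**3. The plan's own figure.** Section 9.4 states 88% power with 113 events, hazard ratio 0.625 and one-sided 0.10. Schoenfeld: √(113/4) × |ln 0.625| - 1.2816 = 5.315 × 0.470 - 1.2816 = 1.217, so power is 0.888. The figure reproduces. The sampling SD of the log hazard ratio is √(4/113) = 0.188.

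**4. How many patients.** The documents give no rate of stopping before progression for this trial. Assumed shares of 67 Arm A patients: 6% (4), 11% (7), 27% (18) and 34% (23). Section 1.3 quotes 6% and 11% from second-line SCLC without chemotherapy. Section 1.2.1.4 quotes 27% from squamous NSCLC monotherapy. The 34% is a further assumption. None of these is a bound for this trial.

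**5. Paired simulation.** The same patients were analysed under equal and unequal schedules.
- From the plan: 67 per arm, 15 months' accrual plus 10 months' follow-up, exponential PFS with medians 5 v 5 and 8 v 5 months, one-sided 0.10.
- Assumed: 15% of events are deaths; an unstratified log-rank test; stops uniform over weeks 3-26, 12-26 or 12-52 and unrelated to prognosis; each scan uniform within ±7 days.
- Size: 288 scenarios of 2,500 trials. Monte Carlo SE of the paired changes is at most 0.0005 (log HR) and 0.4 points (rejection rate).

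| Arm A stopping | Log HR shift |
|---|---|
| 6% | -0.001 to -0.006 |
| 11% | -0.002 to -0.012 |
| 27% | -0.006 to -0.028 |
| 34% | -0.008 to -0.035 |

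All 288 shifts favour nivolumab. Type I error rises by at most 1.2 points at 6-11% and 3.9 points at 27-34%. The worst case, 34% stopping in weeks 3-26, goes from 0.100 to 0.139.

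**6. Check by hand.** A shift of -0.012 is 0.012/0.188 = 0.064 SD, and Φ(-1.2816 + 0.064) = 0.112, a rise of 1.2 points. A shift of -0.035 is 0.186 SD, and Φ(-1.095) = 0.137, a rise of 3.7 points. Both agree with the simulation.

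**7. What moves the result.**
- Every scan on its exact date: the log-rank shift is mixed in sign, -0.016 to +0.015. This comes from ties. At 5 v 5 and 34% stopping the mean shift is -0.002 with exact dates, -0.017 with ±1 day and -0.024 with ±7 days.
- Half of progressions found at unscheduled visits: the shifts halve. At 27-34% stopping they are -0.003 to -0.017, with type I error up 0.5 to 1.7 points.

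**The case against.** The strongest defence is that the plan images both arms to progression and that few patients fall into the affected group. Both statements hold. A reader might infer from footnote 12 that Arm A patients are no longer scanned once treatment stops. Footnote 9 rules that out, and only the spacing is in question.

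A second defence is that Section 6.1 already covers everyone. It counts time on study, and that term is undefined. Footnote 9 treats follow-up as a separate phase. If Section 6.1 includes follow-up, it equalises the arms and conflicts with the footnotes. If it does not, the conflict goes but the difference between arms stays. A reader might call this a flat contradiction, but the text does not settle which reading applies. The open-ended first sentence of Section 6.1 adds little, since the next sentence gives the intervals.

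A reader might also infer that Arm B patients who stop chemotherapy before cycle 4 have no assigned schedule. Section 5.1 sets four cycles as a maximum and sends patients on to observation, so the natural reading keeps them on the dense calendar. This is implied rather than stated. If those patients did move to 3-monthly follow-up at the same 6% or 11% rate, the shift would be only 0.000 to +0.003.

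Finally, an unpaired simulation on exact scan dates, with 2,500 trials per scenario, gave type I error of 0.101-0.107 with the calendar as written and 0.095-0.110 with one calendar, each with a Monte Carlo SE of about 0.006. It could not separate them. That fits a small effect. The paired runs are needed to see it.

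**Conclusion.** The inconsistency is in the current text and touches the primary endpoint, but it is minor. At an assumed 6-11% stopping, the shift of at most 0.012 in log hazard ratio is about one-sixteenth of its sampling SD, and type I error rises by up to about 1.2 points. At an assumed 27-34%, the shift reaches about 0.035 and the rise about 4 points.

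With scan dates spread over the permitted window, the shift favours nivolumab. The figures assume stopping unrelated to prognosis; stopping linked to prognosis could change the size.

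A reader might infer that the PFS comparison is invalid or that the trial is underpowered. Neither follows: the stated power reproduces, and no sample-size figure depends on this point. The confidence here is in the reading of the text. The size rests on stopping rates borrowed from other settings.

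**What to change.** Reconcile Section 6.1 with footnotes 9 and 12:

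- Keep progression-free patients who have not started non-protocol therapy on the same 6/8/12-week scan calendar in both arms, counted from randomisation, whether or not protocol treatment has stopped.
- State that Arm B patients who stop chemotherapy before cycle 4 enter observation on that calendar.
- Define time on study in Section 6.1, so that it is clear whether follow-up is included.

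The interval after non-protocol therapy is already the same in both arms and can stay.

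The cost is a wording amendment. If Section 6.1 is read as not already requiring these scans, it also adds about 0.8 to 2.1 CT time points per affected Arm A patient. That is roughly 3-16 in total at 6-11% stopping and 14-49 at 27-34%. No treatment rule or sample-size figure changes.

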7.2 Biological Sample Submissions

Specimens are to be submitted as outlined in Section [10](#).

All specimens must be entered and tracked via the online ECOG-ACRIN Sample Tracking System (STS).

Biological Materials	Prior to Start of Treatment	Cycle Two (2), Day One (1)	Submit to:
Submit from patients who answer 'Yes' to 'I agree to have my samples collected and I agree that my samples and related information may be used for the laboratory studies.'			
Peripheral Blood (two 10mL Streck Cell-Free DNA tubes)	X	X	CBPF
Submit from patients who answer 'Yes' to 'I agree to provide additional samples for research.'			
Tumor Tissue Biopsy	X		CBPF

1. Kits are being provided for the collection and shipment of the peripheral blood specimens. See [Appendix VII](#) for instructions. Kit orders will on average be delivered within three (3) business days from the time the order is placed.

8. Drug Formulation and Procurement

This information has been prepared by the ECOG-ACRIN Pharmacy and Nursing Committees.

Availability

NCI Supplied Nivolumab – General Information

Drug Ordering: Bristol-Myers Squibb is supplying Nivolumab, through the Division of Cancer Treatment and Diagnosis, NCI, for this protocol. Maintenance of NCI drug accountability records is required. Nivolumab (NSC #748726 and IND#) may be requested by eligible participating Investigators (or their authorized designees) at each participating institution. The CTEP-assigned protocol number must be used for ordering all CTEP-supplied investigational agents. The eligible participating investigators at each participating institution must be registered with CTEP, DCTD through an annual submission of FDA Form 1572 (Statement of Investigator), NCI Biosketch, Agent Shipment Form, and Financial Disclosure Form (FDF). If there are several participating investigators at one institution, CTEP-supplied investigational agents for the study should be ordered under the name of one lead participating investigator at that institution.

Submit agent requests through the PMB Online Agent Order Processing (OAOP) application. Access to OAOP requires the establishment of a CTEP Identity and Access Management (IAM) account and the maintenance of an “active” account status, a “current” password, and active person registration status. For questions about drug orders, transfers, returns, or accountability, call or email PMB any time. Refer to the PMB’s website for specific policies and guidelines related to agent management.

NOTE: Under no circumstances can commercially supplied nivolumab be used or substituted for the NCI-supplied nivolumab.

NOTE: In general, sites may order an initial 5 vials of Nivolumab when a subject is being screened for enrollment onto the study.

Drug Returns: All unused drug supplies must be returned to the PMB. When it is necessary to return study drug (e.g., sealed vials remaining when a patient permanently discontinues protocol treatment, expired vials recalled by the PMB), investigators must return the study drug to the PMB using the NCI Return Agent Form available from the link below, or by calling the PMB at [contact].

Agent Inventory Records: The investigator, or a responsible party designated by the investigator, must maintain a careful record of the receipt, dispensing and final disposition of all agents received from the PMB using the appropriate NCI Investigational Agent (Drug) Accountability Record (DARF) available on the CTEP forms page. Store and maintain separate NCI Investigational Agent Accountability Records for each agent, strength, formulation and ordering investigator on this protocol.

Useful Links and Contacts

- CTEP Forms, Templates, Documents: <http://ctep.cancer.gov/forms/>
- NCI CTEP Investigator Registration: [contact]
- PMB policies and guidelines:
http://ctep.cancer.gov/branches/pmb/agent_management.htm
- PMB Online Agent Order Processing (OAOP) application:
<https://ctepcore.nci.nih.gov/OAOP>

- CTEP Identity and Access Management (IAM) account:
<https://ctepcore.nci.nih.gov/iam/>
- CTEP Associate Registration and IAM account help: [contact]
- PMB IB Coordinator: [contact]
- PMB email: [contact]
- PMB phone and hours of service: [contact] Monday through Friday between 8:30 am and 4:30 pm (ET)

Investigator Brochure Availability

The current version of the IB for Nivolumab will be accessible to site investigators and research staff through the PMB Online Agent Order Processing (OAOP) application. Access to OAOP requires the establishment of a CTEP Identity and Access Management (IAM) account and the maintenance of an “active” account status, a “current” password, and active person registrations status. Questions about IB access may be directed to the PMB IB coordinator via email.

